- Gag reflex or any contraindication to X-ray
- Refusal to participate

5. Interventions

Each participant received:

- Four horizontal bitewing radiographs (control)
- Four vertical bitewing radiographs (experimental)
- Radiographs were taken using a standardized film holder and a 3-mm orthodontic wire attached to the sensor for magnification calibration.

Observers included two restorative specialists (for caries) and two periodontists (for bone loss), all blinded to group assignments.

6. Measurements

- Caries Assessment:

Evaluated using a 5-point diagnostic confidence scale and a secondary clarity scale.

- Bone Loss & Furcation:

Measured from the CEJ to the alveolar crest using calibrated software. Furcation involvement was assessed using a 5-point scale.

- Intra- and Inter-Observer Agreement:

Evaluated with Kappa statistics and intra-class correlation coefficients.

7. Sample Size Calculation

- **Software:** G*Power 3.1.9

- Effect size: 2.1 mean difference

- SD: 5.2

- Power: 80%

- Alpha: 0.05

- Required Sample: 20 patients

8. Statistical Analysis

Statistical Analysis

Software:

Data will be analyzed using IBM SPSS Statistics version 23.0 (IBM Corp., Armonk, NY, USA) and ROC analysis will be performed using MedCalc or equivalent software for diagnostic

accuracy assessment.

8.1 Analysis Population:

All radiographs captured for the 20 enrolled participants (160 total bitewing images: 80 vertical, 80 horizontal) will be included. Both intention-to-treat and per-protocol analyses will be conducted. All images were anonymized, and evaluators were blinded to image type and patient identity.

8.2 Primary Analysis:

Primary Endpoints:

- Detection of approximal caries (presence and clarity)
- Alveolar bone level measurements (in mm)
- Presence and clarity of furcation involvement

Tests for Diagnostic Accuracy:

- **Receiver Operating Characteristic (ROC) Analysis:**

ROC curves were plotted for each evaluator for both vertical and horizontal bitewings.

The Area Under the Curve (AUC) was computed to assess diagnostic accuracy compared to the “gold standard” (combined clinical and radiographic diagnosis).

- AUC values close to 1.0 indicate higher accuracy.
- Comparisons of AUCs between vertical and horizontal bitewings were conducted using DeLong’s test.
- **Sensitivity and Specificity:** These were calculated for each radiographic method in detecting caries and furcation involvement. 95% confidence intervals were provided.

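### Sections 8.1, 8.2 and 8.4 name no unit of analysis and no method for correlation within the 20 patients, and Section 8.4 applies an unpaired chi-square to paired modalities

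*Combined protocol and SAP*

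**What the plan says.** Section 5 gives each participant four horizontal and four vertical bitewings. It describes the readers as follows: "Observers included two restorative specialists (for caries) and two periodontists (for bone loss), all blinded to group assignments". Section 7 counts in patients: "Required Sample: 20 patients". Section 8.1 counts in images: "All radiographs captured for the 20 enrolled participants (160 total bitewing images: 80 vertical, 80 horizontal) will be included".

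Section 8.2 lists caries, bone level in mm and furcation as primary endpoints. On ROC it says "ROC curves were plotted for each evaluator for both vertical and horizontal bitewings", and then "Comparisons of AUCs between vertical and horizontal bitewings were conducted using" DeLong's test. On sensitivity and specificity it says "These were calculated for each radiographic method in detecting caries and furcation involvement. 95% confidence intervals were provided".

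Section 8.4 moves to other units: mesial and distal measurements, tooth type and contacts. It gives bone level to Wilcoxon, caries and furcation presence to McNemar, and overlapping contacts and furcation detection to a chi-square. Section 8.5 speaks of missing image evaluations, and Section 8.6 promises confidence intervals for the AUCs and p-values for their comparison.

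None of these sections names a mixed model, GEE, clustered variance, clustered ROC or McNemar method, patient-level bootstrap, or a rule to summarise to the patient first. The only intraclass correlation in the plan is the observer-agreement statistic.

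**The concern.** Only the 20 patients are independent. Images, teeth and surfaces from one mouth share oral hygiene, disease level, anatomy and ease of positioning. The unit therefore decides the width of every accuracy interval and the size of the p-values, and the plan leaves it open for endpoints it calls primary. Section 9 already expects vertical bitewings to do better, so a unit settled after the data are seen would invite doubt.

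The chi-square is a separate fault that needs no assumed correlation within patients. Every patient has both image types, so comparing the modalities as two independent groups discards the pairing. For furcation the plan supplies a paired and an unpaired test, with no rule on which p-value counts. Overlapping contacts get only the unpaired one.

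**Working it through.** **Inputs from the documents.** 20 patients and 4 images per modality each. The plan's image counts reproduce: 20 × 4 = 80 per modality, and 2 × 80 = 160.

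**Assumed inputs, because the plan gives none.** Units per patient and modality m = 4 (one per image) or 16 (four surfaces per image); prevalence 25% unless stated; sensitivity 0.7; specificity 0.9; disease ICC 0.2; reading ICC 0.05-0.20; share of latent variance due to patient-by-modality differences 0-0.20.

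**1. Sensitivity and specificity intervals.** If units are treated as independent, the variance is understated by DE = 1 + (k − 1) × ICC, where k is the mean number of contributing units per patient. Approximate true coverage is 2Φ(1.96/√DE) − 1. For specificity at 25% prevalence:

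- m = 4: k = 0.75 × 4 = 3. At ICC 0.20, DE = 1 + 2 × 0.20 = 1.4, 1.96/√1.4 = 1.657, coverage 0.902.
- m = 16: k = 0.75 × 16 = 12. At ICC 0.20, DE = 1 + 11 × 0.20 = 3.2, 1.96/√3.2 = 1.096, coverage 0.727.

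Simulated coverage of the naive Wilson interval, which also reflects unequal numbers of units per patient:

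| Reading ICC | 0.05 | 0.10 | 0.20 |
|---|---|---|---|
| Sensitivity, m = 4 | 0.944 | 0.939 | 0.919 |
| Specificity, m = 4 | 0.942 | 0.928 | 0.903 |
| Sensitivity, m = 16 | 0.913 | 0.880 | 0.817 |
| Specificity, m = 16 | 0.883 | 0.820 | 0.712 |

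**2. AUC intervals** (5-point scale, AUC 0.82). Naive coverage at m = 16 is 0.927-0.940 if disease does not cluster, 0.843-0.916 at disease ICC 0.2 and 0.743 at 0.3. At m = 4 it is 0.888-0.925, but part of that shortfall is a small-sample effect.

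**3. Paired comparisons** (nominal type I error 0.05, detection 5-25% for the binary tests).

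| Test on units | Share 0 | Shares 0.05-0.20, m = 4 | Shares 0.05-0.20, m = 16 |
|---|---|---|---|
| McNemar | 0.042-0.057 | 0.048-0.141 | 0.082-0.381 |
| DeLong | 0.047-0.058 | 0.051-0.086 | 0.060-0.237 |
| Chi-square | 0.006-0.036 | 0.016-0.067 | 0.046-0.227 |
| Wilcoxon on sites | – | 0.061-0.118 | 0.139-0.323 |
| Wilcoxon on patient means | – | 0.039-0.053 (both m) | |

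The DeLong maximum of 0.237 is at disease ICC 0.3.

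Share 0 does not guarantee validity when an image carries several surfaces. With 4 surfaces on each of 4 images, no patient-by-modality variation, and image-by-modality shares of 0.05/0.10/0.20, McNemar error is 0.068/0.080/0.109 and chi-square error 0.035/0.043/0.065 at 25% detection. A patient-level t test on the differences stays at 0.049-0.055.

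**4. The chi-square on paired data.** Take 80 independent pairs with correlation φ between the two readings. The unpaired variance is too large by 1/(1 − φ), so true alpha = 2[1 − Φ(1.96/√(1 − φ))]. This gives 0.019, 0.006 and 0.0003 at φ = 0.3, 0.5 and 0.7.

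Power for 25% v 35%, taking φ = 0.45:

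- Both positive: 0.25 × 0.35 + 0.45 × √(0.25 × 0.75 × 0.35 × 0.65) = 0.1804. Discordant: 0.60 − 2 × 0.1804 = 0.2391 (unrounded inputs).
- True SE of the difference: √((0.2391 − 0.01)/80) = 0.0535.
- McNemar null SE: √(0.2391/80) = 0.0547. Power = 1 − Φ((1.96 × 0.0547 − 0.1)/0.0535) = 0.45.
- Chi-square null SE: √(2 × 0.3 × 0.7/80) = 0.0725. Power = 1 − Φ((1.96 × 0.0725 − 0.1)/0.0535) = 0.22.

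Simulation with 4 units per patient and share 0 gives the same picture: 22% against 47%.

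**The case against.** The plan nowhere says that images or sites will be treated as independent, and much of it is sound. McNemar, Wilcoxon and DeLong for correlated curves all respect the vertical-horizontal pairing. Section 8.4 speaks of mean bone loss, which may be one mean per patient; Wilcoxon would then be unaffected. With one unit per image the interval shortfall is modest, and the large figures need 16 surfaces and, for McNemar, the top of the assumed range. All of this stands and limits the point.

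A reader might infer that every p-value in the plan is too small. The documents do not support that. DeLong and McNemar are close to nominal if the modality difference varies neither between patients nor between images. A reader might equally infer that these tests fail only when the difference varies between patients. That is also too strong: with several surfaces per image, error specific to an image is enough. Nor is the chi-square always conservative: ignored pairing and ignored clustering act in opposite directions, and which one wins depends on quantities the plan does not give.

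The choice among patient-clustered methods is partly preference. A stated unit, a method that respects the patient, and one paired test per binary outcome are not.

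**Conclusion.** The point holds as an omission in Sections 8.1, 8.2 and 8.4, together with one wrong test. Confidence in the omission is high. Its size is conditional on assumed ICCs, variance shares and units per patient.

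- Sensitivity and specificity intervals are too narrow whenever readings correlate positively within a mouth: about 90-94% coverage with 4 units, and 71-91% with 16.
- AUC intervals are too narrow mainly when disease also clusters.
- DeLong and McNemar p-values are too small when the modality difference varies between patients or, with several surfaces per image, between images.
- The chi-square loses about half the power of McNemar in the illustration when that variation is absent, and can be liberal when it is large. For furcation it also leaves two competing p-values.

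Bone level in mm may be unaffected. The point does not depend on whether the sample size in Section 7 is right, and it does not extend to the reliability statistics in Section 8.3, which were not assessed. It should be settled before the results are interpreted, because it governs the precision reported for primary endpoints.

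**What to change.** **Section 8.1.** State that the patient is the independent unit, and name the observation for each endpoint: approximal surface for caries, mesial or distal site for bone level, furcation site for furcation, contact for overlap.

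**Section 8.2.** Replace standard DeLong with a clustered-data AUC comparison, for example Obuchowski's method or a bootstrap that resamples patients. Take the AUC, sensitivity and specificity intervals from a patient-clustered variance. Where few patients contribute diseased units, still report the interval if it can be computed, with the counts of units and patients and a caution. Dropping it below some count would remove it too often: with 4 units, fewer than 10 patients contribute diseased units in 19% of simulated trials at 25% prevalence and 98% at 10%.

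**Section 8.4.** Delete the chi-square. Use one patient-clustered paired test of McNemar type for caries, furcation and overlap. Report it for each observer, with a rule stated in advance for which reading, or which combination of the two, is the main result. Keep overlap non-primary, since Section 8.2 does not list it. Run Wilcoxon on one mean difference per patient.

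**Performance and cost.** In simulation, a clustered McNemar test with t on 19 df held type I error at 0.026-0.054, and Obuchowski's comparison with a small-sample t at 0.034-0.060 (25% prevalence). The patient bootstrap was not simulated. With one clustered Wilson interval, widths grow by a factor of about 1.2-1.3 (4 units) or 1.2-1.9 (16 units). Power for 25% v 35% with 4 units falls from 43-47% to 40-44% if the modality difference does not vary between patients. At share 0.1 it falls from 44-47% to 32-34%, where the higher figure comes from a test that does not allow for that variation. The work is SAP wording and a short script outside SPSS; for ROC the plan already allows this ("ROC analysis will be performed using MedCalc or equivalent software"). No new data are needed.

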A Comparison of Horizontal and Vertical Bitewing Radiographs in Detecting Approximal Caries and Interdental Bone Loss in Posterior Teeth: A Diagnostic Accuracy Randomized Cross-Over Clinical Trial

NCT04341636

February 20, 2020

Principal Investigator:

[name]

Departments of Dental Public Health and Periodontology
King Abdulaziz University, Tufts University, Harvard University

Co-Investigators:

[name], [name]
Faculty of Dentistry, King Abdulaziz University

1. Background and Rationale

Bitewing radiographs are a standard diagnostic tool in dental practice, primarily used to detect approximal caries and evaluate interproximal alveolar bone levels. Traditionally, horizontal bitewings have been widely used for these purposes. However, they have limitations in visualizing vertical bone loss, furcation involvement, and root caries.

Vertical bitewing radiographs, by contrast, provide greater visibility of the apico-coronal dimension and root structures, making them potentially more effective for diagnosing periodontal conditions and deeper carious lesions. This study aims to compare the diagnostic accuracy of vertical versus horizontal bitewing images in detecting caries and bone loss in posterior teeth.

2. Objectives

Primary Objective

- To compare the accuracy of vertical versus horizontal bitewing radiographs in detecting approximal caries and alveolar bone loss.

Secondary Objective

- To evaluate the effectiveness of both imaging modalities in identifying furcation involvement.
- To assess the diagnostic clarity and patient suitability for each radiographic approach.

Material and methods:

3. Study Design

This is a two-arm, randomized crossover clinical trial comparing vertical and horizontal bitewing radiographs. The study was conducted at the Faculty of Dentistry, King Abdulaziz University.

Type of Study: Open-label, randomized crossover clinical trial

Study Setting: Faculty of Dentistry, King Abdulaziz University

Registration: ClinicalTrials.gov (NCT04341636)

Ethical Approval: KAU Ethics Committee (#053-06-17)

4. Participants

Inclusion Criteria:

- Age ≥ 18 years
- Presenting for treatment at KAU dental clinics
- Presence of posterior teeth and canines in each quadrant
- No acute periodontal infection
- Non-smokers
- Full ability to open mouth and tolerate X-ray procedures

Exclusion Criteria:

- Systemic conditions complicating treatment
- Pregnancy or lactation
- Prosthesis obscuring CEJ or caries borders

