8.3 Observer Reliability:

- **Intra-Observer Agreement:** Measured using **Weighted Kappa coefficients** for repeated readings of the same radiographs by the same observer at two time points.

- **Inter-Observer Agreement:** Measured using **Intraclass Correlation Coefficient (ICC)** for bone level measurements and **Weighted Kappa** for caries and furcation rating scores between observers.

Interpretation of Kappa values:

- < 0.20: Poor
- 0.21–0.40: Fair
- 0.41–0.60: Moderate
- 0.61–0.80: Substantial
- 0.81–1.00: Almost perfect

8.4 Comparative Tests Between Vertical and Horizontal Bitewings:

- **Wilcoxon Signed-Rank Test:** Used to compare the mean alveolar bone loss measurements (mesial, distal, and total) between vertical and horizontal bitewings (non-parametric paired comparison).
- **McNemar Test:** Applied to assess paired binary outcomes (e.g., presence vs. absence of caries or furcation involvement) between imaging modalities.
- **Chi-Square Test:** Used to compare proportions of overlapping contacts and furcation detection in both modalities.
- **Descriptive Statistics:**
 - Mean \pm standard deviation (SD) for continuous variables (e.g., bone level)
 - Frequencies and percentages for categorical variables (e.g., tooth type, gender distribution)

8.5 Handling of Missing Data:

- Missing image evaluations (if any) were addressed via sensitivity analysis using pairwise deletion, given the minimal expected rate due to controlled data acquisition and blinded

scoring.

8.6 Effect Size Reporting:

- For Wilcoxon and McNemar tests, effect sizes (r) were reported.
- For ROC analysis, 95% CI of AUCs and comparison P-values were provided.

9. Expected Outcomes

- Vertical bitewings will show higher sensitivity in detecting furcation involvement.
- Vertical bitewings will provide better diagnostic accuracy for approximal caries and alveolar bone loss.
- Vertical bitewings will have superior intra- and inter-observer reliability in detecting pathology.

10. Ethical Considerations

- All participants provided informed written consent.
- Ethical approval was secured from local ethics board.
- All data were anonymized and securely stored.
- Participants had the right to withdraw at any time without consequences.

11. Timeline

Phase	Duration
Ethical Approval	Completed
Participant Recruitment	2 months
Radiograph Collection	2 months
Data Analysis	1 month

Phase	Duration
Manuscript	1 month

12. Dissemination Plan

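### Readers cannot be assumed blind to image type, and with no reading order or separation set, the subjective caries, clarity and furcation scores are open to bias in either direction

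*Combined protocol and SAP*

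**What the plan says.** Section 8.1 says that the images carry no identifying details and that "evaluators were blinded to image type and patient identity". Section 5 puts the masking differently: "Observers included two restorative specialists (for caries) and two periodontists (for bone loss), all blinded to group assignments".

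On what the images show, Section 1 says that vertical bitewings "provide greater visibility of the apico-coronal dimension and root structures" compared with horizontal ones.

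On who reads what, Section 5 gives every participant four radiographs of each view. Section 8.2 states that "ROC curves were plotted for each evaluator for both vertical and horizontal bitewings", and Section 8.4 compares the views with paired tests.

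On scoring, Section 6 uses a 5-point confidence scale and a clarity scale for caries, a 5-point scale for furcation, and a software-measured distance for bone level. Section 8.2 lists clarity within two of its three primary endpoints.

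Section 9 records the expected result: "Vertical bitewings will provide better diagnostic accuracy for approximal caries and alveolar bone loss".

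**The concern.** The plan claims masking to image type, but the feature that separates the two views is the anatomy visible on the image. Anonymising removes names and labels and leaves that anatomy in place. Masking to group assignment, as in Section 5, adds little when every participant has both views.

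Two routes to bias follow. A reader who can see which view is on the screen, and who favours one of them, may score it differently. A reader who has already scored one view of a patient may recognise the same restorations or tooth shapes on the other and carry a finding across. Both routes act on judgement scores, which supply the caries and furcation results. A reader of the trial report who takes the blinding statement at face value would discount this risk.

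**Working it through.** **Step 1. Image count.** 20 patients × (4 horizontal + 4 vertical) = 160 images, 80 per view. This matches Section 8.1 and confirms that every patient contributes both views.

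**Step 2. Is masking to image type achievable as described?** Section 8.1 claims it. Section 1 says the vertical view shows more height and root. The readers are restorative specialists and periodontists (Section 5). No cropping, re-orientation or other masking step appears anywhere. That the view is recognisable is an inference, but it follows from the plan's own account of how the views differ.

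**Step 3. Do the same readers score both views?** Section 8.2 gives each evaluator a ROC curve for each view, and Section 8.4 pairs the views. Together these imply that they do.

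**Step 4. Is anything set that limits carry-over?** No reading order, separate sessions or interval between views is stated. The two time points in Section 8.3 concern rereading the same radiograph for intra-observer agreement, and no interval is given. The crossover randomisation in Section 3 is not described as covering reading order.

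**Step 5. What could a reader shift do?** The documents give no AUC and no size of shift, so both are assumed here. Take normally distributed ratings with SD 1 in diseased and in sound surfaces, and a true AUC of 0.80 for both views. The true difference between views is then zero.

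AUC = Φ(d/√2), so d = √2 × 0.8416 = 1.190. A shift of *a* in diseased and *b* in sound surfaces on one view changes d to 1.190 + a − b.

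| Shift in diseased (SD) | Shift in sound (SD) | New d | AUC on that view |
|---|---|---|---|
| 0.10 | 0 | 1.290 | 0.819 |
| 0.25 | 0 | 1.440 | 0.846 |
| 0.50 | 0 | 1.690 | 0.884 |
| 0.25 | 0.25 | 1.190 | 0.800 |
| 0.50 | 0.50 | 1.190 | 0.800 |
| 0.10 | 0.25 | 1.040 | 0.769 |

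The first three rows describe a selective shift, such as a true finding carried over from the other view. The next two describe a reader who scores one view higher throughout without knowing which surfaces are diseased. The last shows that the error can also lower the AUC.

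**Step 6. Does an unchanged AUC mean no harm?** Assume a positive call above a fixed cut-off midway between the two means, at 1.190/2 = 0.595. Without a shift, sensitivity = Φ(0.595) = 0.724 and specificity = Φ(0.595) = 0.724. With +0.25 SD in both groups:

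- sensitivity = Φ(0.595 + 0.25) = Φ(0.845) = 0.801
- specificity = Φ(0.595 − 0.25) = Φ(0.345) = 0.635

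Positive calls rise by 7.7 percentage points in diseased surfaces (72.4% to 80.1%) and by 8.9 points in sound ones (27.6% to 36.5%). The proportion called positive on that view therefore rises at any prevalence. The McNemar comparison of presence against absence responds to exactly this, although AUC has not moved.

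**The case against.** The strongest case on the other side has five parts.

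- **The size is assumed.** The AUC of 0.80 and the shifts come from no section of the plan, and the simplest expectation effect leaves AUC unchanged. This stands: the figures show what could happen and are not an estimate.
- **Reader expectation is inferred.** Section 9 gives the investigators' expected results, and nothing says that the four readers knew them. This stands as a limit. Nothing describes shielding readers from that expectation either, and the memory route does not depend on it.
- **A silent protocol does not show that the views were read together.** This is correct. A reader might infer from the missing reading order that both views of a patient were scored side by side, or that bias did occur. The documents support neither. Using the same readers for both views is also not a flaw in itself, because the paired per-reader comparison needs it.
- **The comparison as a whole is not equally exposed.** A reader might infer that every endpoint is compromised. Bone level is measured from CEJ to crest with calibrated software and a 3-mm reference wire, which leaves less room for expectation.
- **Anonymising limits recall.** It does so by name, but not by recognition of anatomy.

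These points narrow the scope and remove any claim to a known size. They do not rescue the statement in Section 8.1, which goes beyond what anonymising the images can deliver.

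**Conclusion.** The point holds in limited form. The plan claims masking to image type, and its own description of the views makes that claim untenable without a masking step, which it does not describe. Because the same readers score both views with no order or separation set, expectation or memory can bias the subjective scores. The direction is not fixed. Expectation would tend to favour the vertical view. Memory would favour whichever view is read second if the order is fixed, and would shrink the difference if the order is balanced.

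The size cannot be computed from the documents. The Step 5 and 6 figures rest on normal ratings and an assumed shift, and Step 6 also on an assumed cut-off. They show that modest shifts can produce an apparent difference where none exists, and that a stable AUC would not rule out bias in the other results. The change should be made, but the finding does not show that the trial's comparison is invalid.

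**What to change.** 1. In Sections 5 and 8.1, withdraw the claim of blinding to image type. Claim only masking that is actually arranged: patient identity and the scores from the other view. Add clinical findings and the reference diagnosis only if readers are in fact kept apart from them. The plan does not say who makes the combined reference diagnosis, so this has to be settled before it is stated.
2. Read the two views of a patient in separate sessions, with image order and first view randomised for each reader and a fixed interval between sessions.
3. Keep clarity within the primary endpoints as Section 8.2 lists it. The confidence and furcation scores are subjective too, so the limitation should be stated for all of these scores and not for clarity alone.
4. If reading is already complete, as the past tense in Sections 5 and 8 may suggest, correct the masking claim, report the actual reading order and state the limitation for all subjective scores.

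**Cost.** A longer reading calendar and a weaker masking claim. If reading has not started, the sessions need no extra readers or images, and each image is still scored as often as planned. If reading is finished, separate sessions would mean rereading, which is why item 4 relies on disclosure. The two time points in Section 8.3 should not be counted on to supply these sessions, because the plan does not say that all 160 images are reread.

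### Furcation and clarity are secondary in Section 2 but primary in Section 8.2, and the plan states no success rule, multiplicity rule or complete lead analysis for its primary endpoints

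*Combined protocol and SAP*

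**What the plan says.** **Status of the endpoints.** The primary objective in Section 2 is "To compare the accuracy of vertical versus horizontal bitewing radiographs in detecting approximal caries and alveolar bone loss". The secondary objectives there are "To evaluate the effectiveness of both imaging modalities in identifying furcation involvement" and "To assess the diagnostic clarity and patient suitability for each radiographic approach". Section 8.2 lists three primary endpoints: "Detection of approximal caries (presence and clarity)", alveolar bone level in mm, and "Presence and clarity of furcation involvement". The title and the aim at the end of Section 1 name only caries and bone loss. Section 6 calls the caries clarity scale secondary. Section 9 puts furcation sensitivity first among its expected outcomes.

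**Analyses.**
- Section 8.2 is headed Primary Analysis and contains ROC/AUC with DeLong's test: "ROC curves were plotted for each evaluator for both vertical and horizontal bitewings". It also contains sensitivity and specificity: "These were calculated for each radiographic method in detecting caries and furcation involvement".
- Section 8.4 adds Wilcoxon for bone, "Used to compare the mean alveolar bone loss measurements (mesial, distal, and total) between vertical and horizontal bitewings", McNemar for caries or furcation, and chi-square for furcation detection and overlapping contacts.
- Section 8.1 calls for both intention-to-treat and per-protocol analyses and ranks neither.

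**Error control.** Section 7 gives one alpha, 0.05, with 80% power and 20 patients. It names no endpoint and no sidedness. No section gives a success rule, a testing order or a multiplicity adjustment.

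**The concern.** Two gaps combine. First, a reader cannot tell whether a furcation or clarity result would be confirmatory, because Sections 2 and 8.2 give different answers. Second, even for caries and bone loss the plan does not say which statistic decides the objective, or whether success on one target is enough. As written, any of several tests at the 0.05 level could be presented as the primary result.

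The missing rule matters on either reading. If any one win counts, the chance of a false primary claim exceeds 5%. If all must win, error is protected, but the chance of meeting the primary objective is below the power of each single test. Section 9 joins caries and bone loss in one expectation, without a threshold, and fits either reading.

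**Working it through.** **1. The sections side by side.**

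| Item | Section 2 | Section 8.2 |
|---|---|---|
| Approximal caries, presence | primary | primary |
| Alveolar bone | primary | primary |
| Furcation | secondary | primary |
| Clarity | secondary | part of two primary endpoints |

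The clarity conflict is the softer one, since Section 2 could mean overall image quality.

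**2. Is a lead analysis named?**
- *Caries:* AUC by DeLong's test is a fair reading, from the heading of 8.2. It is run per evaluator, with two restorative readers (Section 5) and no rule for combining them. It is not ranked against sensitivity and specificity. McNemar follows in 8.4.
- *Bone:* no cut-off turns mm into a diagnosis for a ROC curve. The only between-modality test named for it is Wilcoxon, on three measures with none first.
- *Furcation:* sensitivity and specificity, McNemar and chi-square. ROC is not excluded, since Section 6 gives furcation a 5-point scale.

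**3. The plan's only related figure.** From Section 7, d = 2.1/5.2 = 0.404. If 5.2 is the SD of paired differences (an assumption), an exact two-sided paired t-test needs 51 patients for 80% power, and 20 patients give 40%. The stated 20 does not reproduce on that reading. That is a separate matter, but it means the cost in step 6 must be shown from both 80% and 40%.

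**4. Any win counts.** Assume one two-sided test per endpoint at 0.05. For k independent tests the familywise error is 1 − 0.95^k:
- k = 2: 1 − 0.9025 = 0.0975
- k = 3: 1 − 0.857375 = 0.1426

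For k normal statistics with common correlation ρ it is 1 − ∫ φ(u) [Φ((1.96 − √ρ·u)/√(1−ρ)) − Φ((−1.96 − √ρ·u)/√(1−ρ))]^k du.

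| Endpoints | ρ = 0 | ρ = 0.5 | ρ = 0.9 |
|---|---|---|---|
| 2 (Section 2) | 9.75% | 9.1% | 7.0% |
| 3 (Section 8.2) | 14.3% | 12.5% | 8.4% |

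**5. All must win.** Suppose each test has 80% power. Under independence, joint power is 0.8² = 0.64 and 0.8³ = 0.51. With correlation it is ∫ φ(u) Φ((0.84 + √ρ·u)/√(1−ρ))^k du, where 0.84 = 2.80 − 1.96.

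| Endpoints | ρ = 0 | ρ = 0.5 | ρ = 0.9 |
|---|---|---|---|
| 2 | 64% | 69% | 75% |
| 3 | 51% | 61% | 72% |

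**6. Power cost of Holm.** Paired t as an approximation to Wilcoxon, n = 20, two-sided. Holm powers are simulated with 100,000 trials and the same effect on every target. The effect d = 0.660 is the one that gives 80% power at 0.05.

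| Effect | Unadjusted 0.05 | Targets | Per-target Holm, ρ = 0 / 0.5 / 0.9 | One test at 0.05/k |
|---|---|---|---|---|
| d = 0.660 | 80% | 2 | 77 / 76 / 74% | 70% |
| d = 0.660 | 80% | 3 | 74 / 72 / 70% | 63% |
| d = 0.404 | 40% | 2 | 32 / 32 / 33% | 29% |
| d = 0.404 | 40% | 3 | 27 / 28 / 28% | 24% |

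The last column is the Bonferroni power of a single test. Holm comes close to it only when no other target has an effect.

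**The case against.** **The plan does name a primary method.** Section 8.2 is headed Primary Analysis and contains ROC/AUC with DeLong's test, while Wilcoxon, McNemar and chi-square sit apart in 8.4. A reader might infer that there is no lead analysis at all. The documents do not support that for caries. What stands is narrower: no reader rule, no ranking against sensitivity and specificity, no lead for bone or furcation, and no lead analysis set.

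**The furcation question is nearly answered.** The title and the Section 1 aim agree with Section 2. The order of bullets in Section 9 is weak counter-evidence, since its third bullet is reliability, which no section calls primary. So the documents lean towards Section 2, and a reader should not infer that they are evenly balanced. They still do not settle the matter, because 8.2 is explicit.

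**The error figures are hypothetical.** This is fair. A reader might infer that the trial has a 14% false-positive rate. The plan states no any-win rule, so that rate is not established. The joint-power figures likewise assume 80% per endpoint, which Section 7 ties to no endpoint.

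**Adjustment might look more costly than it is.** A reader might take 70% and 63% as the power under Holm. They are single-test Bonferroni powers and mark its worst case.

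**Conclusion.** The point holds. Sections 2 and 8.2 contradict each other on furcation and, on the natural reading, on clarity. Three primary endpoints share one alpha of 0.05 with no success rule, testing order or adjustment. The lead analysis is partly identifiable for caries and is not settled for bone or furcation.

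The consequence is an undefined primary claim. Its possible size, with one test per endpoint at 0.05 and equal correlations, is a familywise error of 8.4% to 14.3% for three endpoints, or 7.0% to 9.75% for two, if any win counts. If all must win, there is no inflation but there is a loss of joint power. Because 8.2 and 8.4 offer several tests per endpoint, the any-win figures would be too low if any of those tests could carry the claim. The plan should be corrected on this point; the correction is mainly to the text.

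**What to change.** 1. **Align the sections.** Make caries and bone loss the only primary targets in 8.2, and move furcation and clarity to secondary. If the sponsor intends furcation to be primary, amend Section 2, name one lead furcation analysis and include it in the adjustment.
2. **Name one lead analysis, reader rule and analysis set per target.**
   - *Caries:* the vertical-minus-horizontal AUC difference averaged over the two restorative readers, tested by a method that accounts for the covariance between readers of the same images. Separate per-reader DeLong p-values do not test that average. Another pre-stated reader rule would also serve.
   - *Bone:* one total measure per patient per modality, averaged over the two periodontists, by the planned Wilcoxon test. If a reference bone level in mm exists, compare absolute errors against it, to match the accuracy wording of Section 2. If none exists, reword the bone objective as a between-modality difference.
   - All other tests are supportive, reported with confidence intervals and no confirmatory claim.
3. **State the success rule.** Either Holm at overall two-sided 0.05 (two targets: 0.025, then 0.05; three: 0.0167, 0.025, 0.05), or a fixed order stated in advance.

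**Cost.** Text changes to Sections 2, 8.1, 8.2 and 8.4. No new data are needed, unless a reference bone level in mm is wanted and was not recorded. Taking the plan's 80% as correct and every target as having that effect, per-target power under Holm is about 74–77% with two targets or 70–74% with three; the worst case is near 70% or 63%. If 5.2 is the SD of paired differences, it falls from 40% to about 32–33% or 27–28% (worst case near 29% or 24%). The cost for the caries AUC cannot be computed from the documents. A fixed order avoids the smaller threshold, but the second target then depends on the first.

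Much of Sections 8.2 to 8.6 is in the past tense. If results are already known, the change must be dated and disclosed as post hoc.
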